## 2.0 FLOW CHARTS

### 2.1 Enrollment process

[figure not shown]

Figure 1 Enrollment process

## 2.2 Study flow chart

[figure not shown]

Figure 2 Study flow chart

### 2.3 Visit schedule

[figure not shown]

Figure 3 Visit schedule

---

## 4.0 TRIAL IDENTIFIER

### 4.1 Full title of trial

Management of acute lateral ankle sprains: A randomized, controlled trial

### 4.2 Short title

Management of acute lateral ankle sprains

### 4.3 Acronym

Pending

### 4.4 Health Research Ethics Committee Number

SJ-628

### 4.5 Trial registration identifier and date

Pending

### 4.6 Version number and date

Version 1.0 (first draft for committee review; pre-authorisation version)

Version 1.1 (Updated with changes, as specified by the secretary, before presentation to the health research ethics committee)

Version 1.2 (Updated with changes, as specified by the regional health research ethics committee)

Version 1.3 (Updated with changes, as specified by reviewers from [www.clinicaltrials.com](http://www.clinicaltrials.com))

### 4.7 Revision history

Version #	Issue date	List of major changes
1.0	May 29, 2017	This is the first draft
1.1	June 8, 2017	All questionnaires will be translated to Danish before trial start.  The Study will be carried out following “The Act on Processing of Personal Data”  All positive, negative or inconclusive results will be published at www.clinicaltrials.gov .

1.2	July 25, 2017	[name] is included in the study committee. The economic properties for this study is included in the written information.
1.3	May 3, 2018	Translated all information to English before publication on www.clinicaltrials.com . Updated the first page to include the unique Human Subjects Review board number: SJ-628 and date. [name] has withdrawn his participation in this study and thus removed from the protocol development committee.

#### 4.8 Sponsor

The Department of Physiotherapy and Occupational Therapy, Næstved-Slagelse-Ringsted Hospitals.

## **5.0 BACKGROUND INFORMATION**

Lateral ankle sprains (LAS) is the most common injury in the active population. Not only is the injury prevalent within organized sports, but also display high prevalence in the general population presenting at the emergency departments (ED). LAS accounts for about 3-5% of all visits to the ED, but total LAS incidence rates are increasing in the general population.

Acute LAS is defined by Delahunt et al. and endorsed by the International ankle consortium^9 as: *“An acute traumatic injury to the lateral ligament complex of the ankle joint as a result of excessive inversion of the rear foot or a combined plantar flexion and adduction of the foot.”*

The treatment of LAS in the emergency department consists of initial assessment and acute management of the injured foot, traditionally done by a physician. The typical assessment consists of ruling out severe injury, i.e. fracture, using the Ottawa ankle foot rules. The acute management of the injured ankle is typically composed of a treatment approach consisting of Rest, Ice, Compression and Elevation (RICE).

Extended Scope of Practice (ESP) physiotherapists in EDs have shown to generate high levels of patient satisfaction, reduce patient waiting times and have high clinical effectiveness, yet high quality randomized trials investigating the clinically effectiveness of ESP physiotherapy are lacking. Acute LAS is one of the most common injuries managed in EDs and poor functional status within the initial 2 weeks after injury is predictive of development of chronic ankle instability (CAI), which can be a serious barrier for future physical activity and occupational performance. Early and targeted interventions provided in the emergency department by ESP physiotherapists may therefore prove to be beneficial for the patients and the society.

We therefore propose this trial that aims to assess the effectiveness of ESP physiotherapy as a mean to enhance the outcome of acute LAS following presentation to an emergency department.

## **6.0 STUDY HYPOTHESIS**

### **6.1 Hypothesis**

The functional outcome following presentation to an ED with an acute LAS is superior when managed by an ESP physiotherapist compared to usual procedures.

## **7.0 STUDY DESIGN**

### **7.1 Description of the protocol**

This is a randomized, pragmatic, superiority study with 1, 2, 3 and 4 weeks, and 3, 6 and 12 months of follow-up (figure 2). The study will be carried out in the emergency department at 22

large public hospitals in Slagelse and Horsens, Denmark. Two-hundred-twenty-six adults with an acute lateral ankle sprain will be included in this study.

The participants will be randomly allocated to one of two treatment strategies:

**Strategy A:** A single session with advice and instructions from an ESP physiotherapist in rest, ice, compression and elevation AND pain guided early weight bearing plus a written home-based exercise program (ESP physiotherapy group).

or

**Strategy B:** A single session with advice and instructions from a physician in rest, ice, compression and elevation (usual care).

The randomized allocation will be equal (1:1).

### **7.1.1 Justification of a pragmatic trial design**

The pragmatic trial design has the benefit of making employees and decision-makers in the emergency department aware of the protentional benefits in early weight bearing and exercise in the large group of people presenting with an acute LAS. Participants receiving information and advice from a physiotherapist in the emergency department, will be giving instructions in early weight bearing and exercise and the participants receiving usual care will not, because it is the effects of these two strategies, when administered in the emergency department, we want to compare. The pragmatic design means that the trial will provide valuable information that will help clinicians and decision-makers decide if advice from a physiotherapist in the emergency department improves the clinical outcomes of acute LAS.

### **7.2 Duration of study participation**

The study's duration is 12 months after randomization.

## **8.0 SELECTION AND ALLOCATION OF PARTICIPANTS**

### **8.1 Number of participants planned**

It is anticipated that 226 participants will be enrolled in this study. A participant may be enrolled in this study provided he/she has met all the inclusion criteria and has not met any of the exclusion criteria.

### **8.2 Inclusion Criteria**

An individual will be eligible for study participation if he/she meets the following criteria:

1. A grade 1 or 2 LAS sustained within 24 hours of randomization
2. To be a minimum age of 18
3. Signed informed consent

### **8.3 Exclusion Criteria**

A participant will be excluded from the study if he/she meets any of the following criteria:

1. A grade 3 LAS injury sustained
2. Diagnosed with chronic ankle instability (CAI) on the affected limb
3. Fracture diagnosed by X-ray
4. Previous enrollment in the same study
5. Major lower limb surgery or other severe lower extremity injury in the past 3 months on the affected limb
6. Under the influence of drugs or alcohol
7. A condition that, in the opinion of the investigator, would preclude participation in the study (e.g., not having access to the internet, immobilization etc.)

#### **8.3.1 Grading of LAS**

The grading of each patient is following Standard Operating Procedures (S.O.P.) (Appendix 1).

- 1.° LAS (At present the patient can bear weight)
- 2.° LAS (Pronounced limping, major pain)
- 3.° LAS (The patient cannot bear weight on the foot)

### **8.3.2 Chronic ankle instability**

The participant should report a minimum of one major LAS injury sustained a minimum of 12 months prior to assessment for eligibility of enrolment in the study. After this injury, the participant should have experienced the classical signs of decreased function and swelling.

Participants should report at least two episodes of ‘giving way’ or have sustained two or more ankle sprains to the same ankle in the 6 months prior to the study enrolment to be diagnosed with CAI.

We endorse the definition of giving way as: *“The regular occurrence of uncontrolled and unpredictable episodes of excessive inversion of the rear foot (usually experienced during initial contact during walking or running), which do not result in an acute lateral ankle sprain”*.

## **8.4 Allocation of participants and sequence generation**

We will stratify the randomization by

- Site (2 levels; Slagelse Hospital and The Regional Hospital in Horsens)

The allocation ratio will be 1:1.

Randomization lists will be computer-generated based upon permuted random blocks of variable size (3 to 6 in each block).

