## **8.5 Blinding**

Data analysts will be blinded to treatment allocation.

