### **15.2 Oral information**

When a potential participant is identified during initial assessment in the ED he/she will be given information about this trial. If further investigations are needed to determine eligibility for enrollment, the information will be given after completion of these. It will be stressed that the investigator is asking the participant to consider participation in the trial, and that the potential

trial participant has the right to bring a companion to the information interview, if possible. The written information material will be handed out in the ED by the trial investigator. The participants will not be able to have a 24-hour consideration period before inclusion in the study, but will have sufficient time to consider inclusion. The oral information will be given in a language easily understood without technical or value-laden terms. The information will be given in a considerate way that is tailored to each potential trial participants. The conversation will take place without interference. It is the responsibility of the interviewer to ensure that the potential trial participant has understood all the information giving. Guidelines for the oral information are given in Appendix 6.

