## **16.0 CASE REPORT FORM COMPLETION**

### **16.1 Case Report Forms**

The study will use electronic CRFs using an online web-based clinical trial management application (EasyTrial). EasyTrial allows individual patients to supply data from home.

The application meets all regulatory standards, and allows management of all activities related to clinical trials that ensures optimal resource use and safety according to good clinical practice and data protection legislation.

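### Section 8.4 prints small, site-level block sizes in an open trial, so a recruiter who sees past assignments could guess the next one about 65–69% of the time

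*Combined protocol and SAP*

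**What the plan says.** Section 8.4 sets the allocation: "The allocation ratio will be 1:1", with one stratification factor, "Site (2 levels; Slagelse Hospital and The Regional Hospital in Horsens"), and the block rule "Randomization lists will be computer-generated based upon permuted random blocks of variable size (3 to 6 in each block"). It does not say which sizes within that range are used, or how a block of 3 or 5 is split under equal allocation.

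Section 8.5 names one blinded party: "Data analysts will be blinded to treatment allocation". Sections 7.1, 9.1 and 9.2 make the arm visible in the emergency department (ED), because it decides whether a physician or an ESP physiotherapist gives the session and whether an exercise program is handed out.

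Entry involves some judgement. Section 8.3 excludes patients with "A condition that, in the opinion of the investigator, would preclude participation in the study". Section 8.3.1 separates an eligible grade, "2.° LAS (Pronounced limping, major pain"), from an excluded grade by whether the patient can bear weight. Under section 15.2 the investigator approaches patients: "The written information material will be handed out in the ED by the trial investigator".

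Section 12.3 lists the inclusion/exclusion review first and randomization fourth. It puts baseline procedures before allocation, whereas sections 10.3 and 12.2 put baseline data after randomization. Section 16.1 says that EasyTrial "allows management of all activities related to clinical trials" but does not mention randomization.

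**The concern.** With permuted blocks, an arm that is behind within a block becomes more likely to come next. The smaller the block, the stronger this signal. Three features here allow it to be read and used: each site has its own list, past assignments can be seen from who treated the patient, and the block range is printed in the protocol.

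A recruiter who expects a given arm could, knowingly or not, lean on the discretionary exclusion or the grading boundary. The two groups would then differ in prognosis before treatment starts. The primary outcome, change in LEFS at 4 weeks, would carry that difference into the treatment comparison. Blinding the analysts does not remove it.

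**Working it through.** **Inputs from the documents.** Blocks of 3 to 6, 1:1, by site (8.4). 226 patients (8.1, 13.1). Difference of 9 LEFS points, SD 19, power 90%, alpha 0.05, 94 per group (13.1). Two-sided tests (13.5).

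**Assumptions.** Equal recruitment, so 226/2 = 113 patients per site list. Two readings of the block rule: sizes 3/4/5/6 equally likely, with the odd slot by coin toss, or sizes 4 and 6 only. The share of past assignments seen and the steering size v are not in the documents, so both are varied. Section 13.1 gives the SD with reference to 6 months; applying it at week 4 is also an assumption.

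**1. The plan's own figure.** n = 2 × (1.960 + 1.282)² × 19² / 9² = 2 × 10.51 × 361 / 81 = 93.7, so 94 per group. This reproduces. The standard error is 19 × √(2/94) = 2.77 points.

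**2. Hand check with block boundaries known.** For an even block of 2m, the share of correct guesses is [m + (4^m / C(2m, m) − 1)/2] / 2m.
- Size 4: (2 + 0.833)/4 = 0.708.
- Size 6: (3 + 1.1)/6 = 0.683.
- Sizes 3 and 5 with a coin-toss slot, by enumeration: 0.611 and 0.620.
- Weighted by size, 4/6: (4 × 0.708 + 6 × 0.683)/10 = 0.693.
- Weighted by size, 3/4/5/6: (3 × 0.611 + 4 × 0.708 + 5 × 0.620 + 6 × 0.683)/18 = 0.659.

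**3. Block boundaries unknown.** This is a simulation of a best guesser who knows the set of sizes but not the size of each block.

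| Earlier site assignments seen | Sizes 3/4/5/6 | Sizes 4/6 |
|---|---|---|
| 100% | 64.7% | 69.2% |
| 75% | 60.9% | 62.4% |
| 50% | 57.9% | 58.8% |
| 25% | 54.2% | 54.5% |

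With everything seen, the next assignment is certain for only 0.3% and 5.6% of patients respectively. If the range meant patients per arm (blocks of 6/8/10/12), the rate would be 65.4%.

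**4. What printing the sizes adds.** The rule of guessing the arm with fewer patients so far needs no knowledge of block sizes. With everything seen it is right 57.3% of the time for 3/4/5/6 and 69.1% for 4/6. Against this rule, disclosure adds about 7 percentage points in the first case (64.7 − 57.3) and almost nothing in the second.

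**5. Consequence if every patient is steered.** If steering shifts prognosis by ±v according to the guess, and g is the share of correct guesses, the bias is 2v(2g − 1). The two-sided error rate is Φ(−1.96 + bias/2.77) + Φ(−1.96 − bias/2.77).

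| v (assumed) | g | Bias, LEFS points | Error rate |
|---|---|---|---|
| 1 | 0.65 | 2 × 0.30 = 0.60 | 5.5% |
| 1 | 0.69 | 2 × 0.38 = 0.76 | 5.9% |
| 2 | 0.65 | 4 × 0.30 = 1.20 | 7.2% |
| 2 | 0.69 | 4 × 0.38 = 1.52 | 8.5% |
| 2 | 0.54 | 4 × 0.08 = 0.32 | 5.2% |

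The largest value, 1.52 points, is 1.52/9 = 17% of the difference the trial is powered to detect.

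**The case against.** Several stronger readings are tempting, and the documents do not support them.

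- **That the plan has no allocation concealment.** The readable text does not say who holds the list or how an assignment is released. However, Figure 1, on the enrollment process, is not shown and may cover this. Nothing suggests that recruiters can consult the list.
- **That eligibility is left open until after allocation.** Section 12.3 puts the eligibility review before randomization, and section 8.2 makes signed consent an entry criterion. The conflict with 10.3 and 12.2 concerns when baseline data are taken. What the readable text lacks is a statement that eligibility is saved as final before the assignment appears.
- **That disclosure of the sizes is the main problem.** Step 4 shows otherwise for even blocks. Small site-level blocks combined with visible treatment are the main driver.
- **That recruiters know every past assignment, or that the treating physiotherapists recruit.** Neither is stated. With partial knowledge the rate falls to 54–62%.
- **That steering would be undetectable.** Section 12.3 collects the outcomes at baseline, and section 10.3 and Appendix 4 add previous sprain and time since injury. Imbalance can therefore be examined, though not conclusively.

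It is also fair to say that grading follows a standard procedure, and that the investigator-opinion exclusion comes with examples that limit its scope. Because the outcome is a change score on a scale capped at 80, enrolling milder patients also raises their baseline, so even the direction of bias is uncertain. The ±v shift has to be read as a shift in the change score itself.

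What remains is the printing of small, site-level block sizes in an open trial where entry is partly discretionary.

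**Conclusion.** The point holds as a modest, cheaply reduced weakness. The next assignment could be guessed about 65–69% of the time by someone who sees all earlier assignments at the site, and about 54–62% by someone who sees 25–75% of them. Under assumed steering of every patient by ±1 to ±2 LEFS points, the 65–69% range gives a bias of about 0.6–1.5 points and an error rate of about 5.5–8.5%. The guess rates rest on the two readings of the block rule and on 113 patients per site. The bias figures rest also on the steering size and on using SD 19 at week 4. Whether steering would occur, and how large it would be, cannot be derived from the documents, so this is a reason for a safeguard and not evidence of bias.

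**What to change.** 1. Delete the bracketed block-size range from 8.4 and from site documents. Hold the sizes, including how any odd block is split, in a restricted randomization file. Under the literal 3-to-6 rule, this lowers predictability from about 65% to about 57% for someone using the fewer-so-far rule. Staff who have already read this version know the range, so the gain is smaller unless the sizes also change.
2. Unless Figure 1 already specifies it, add to 8.4 that assignments are shown one at a time, and only after consent and all eligibility answers, including LAS grade, are saved as final. Reconcile 12.3 with 10.3 and 12.2 on the timing of baseline data.
3. Consider larger or less predictable blocks, because for sizes 4 and 6 hiding the range leaves about 69%. With all site assignments seen, simulated rates are 65% for blocks of 8/10/12, 61% for 16/20/24, and 56% for a big-stick rule with an imbalance limit of 4.

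The cost is restricted filing, a wording change and a login step before allocation in the ED. No extra patients or visits are needed. That EasyTrial can release assignments in this way is an assumption; otherwise an equivalent central list would be needed. Larger blocks allow somewhat more imbalance in numbers within a site.

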## **13.0 DETERMINATION OF SAMPLE SIZE AND STATISTICAL ANALYSIS PLAN**

### **13.1 Determination of Sample Size**

The study will be powered to detect a difference in change of 9 points between the two groups in the primary outcome (LEFS) from baseline to 6 months follow-up. The 9 point change has previously been recommended and applied in similar studies as the minimal clinically important difference in LEFS. To detect this difference, we will need 94 patients in each group (assuming a common SD of 19, power = 90%, alpha level = 0.05). We plan to recruit 226 patients to account for loss to follow-up (20%).

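### Do block sizes of 3 to 6 undermine 1:1 allocation between two arms?

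*Combined protocol and SAP*

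**What the plan says.** Section 7.1 describes a two-arm trial: "The participants will be randomly allocated to one of two treatment strategies", and "The randomized allocation will be equal (1:1". Section 8.4 repeats the ratio ("The allocation ratio will be 1:1") and stratifies by one factor, "Site (2 levels; Slagelse Hospital and The Regional Hospital in Horsens". It then specifies computer-generated lists based on "permuted random blocks of variable size (3 to 6 in each block". No section restricts the sizes to even numbers or explains how an odd block is divided, and the revision history in section 4.7 records no change to randomization. On blinding, section 8.5 says only "Data analysts will be blinded to treatment allocation".

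**The concern.** A permuted block normally contains the arms in the allocation ratio, so the counts are level each time a block closes. With two arms at 1:1 this needs an even size. Section 8.4 names 3 as its smallest size, and a block of 3 can only split 2:1. If 5 is also used, it can only split 3:2. The stated ratio and the stated sizes therefore cannot both hold inside every block, and the rule that would settle the matter is not given.

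If this were a real fault, the list could drift from 1:1, balance within each hospital could be lost, and power could fall. Someone checking the list against the protocol would also have no rule to check it by.

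**Working it through.** **Inputs.** From the documents: two arms, 1:1, two sites, 226 patients, block sizes 3 to 6 (sections 7.1, 8.1, 8.4); difference 9, SD 19, power 90%, alpha 0.05, 20% loss (section 13.1); two-sided tests (section 13.5). Assumed, because the documents do not say: sizes 3, 4, 5 and 6 equally likely, and 113 patients per site.

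**1. The plan's own sample size.** Section 13.1 states "we will need 94 patients in each group (assuming a common SD of 19, power = 90%, alpha level = 0.05". With the normal formula, n = 2 × (1.960 + 1.282)² × 19² / 9² = 93.7, so 94 per group. The figure is reproduced and does not depend on the block scheme.

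**2. Which rule for the extra place fits the text?**
- *Always the same arm.* Over one block of each size that arm receives 2 + 2 + 3 + 3 = 10 of 18 places, a ratio of 5:4. This contradicts the 1:1 stated in sections 7.1 and 8.4, so the text excludes it.
- *Chosen at random for each odd block.* The arms are then interchangeable, each patient has probability 1/2 of either arm, and the ratio is 1:1 in expectation. This fits everything the protocol says.

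**3. How much imbalance does the random rule allow?** Each completed odd block adds +1 or -1 to the difference between arms; each completed even block adds 0. The mean block size is (3 + 4 + 5 + 6)/4 = 4.5.
- Per site: 113/4.5 = 25.1 blocks, about 12.6 of them odd, so SD ≈ √12.6 = 3.5.
- Whole trial: 226/4.5 = 50.2 blocks, about 25.1 odd, so SD ≈ √25.1 = 5.0.

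Simulation of 20,000 trials, which includes the last incomplete block, gives slightly larger values:

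| Scheme | SD per site | SD whole trial | 95% range, whole trial | Guess of lagging arm correct |
|---|---|---|---|---|
| Sizes 3–6, random extra place | 3.7 | 5.2 | -10 to +10 | 57% |
| Sizes 4 and 6 | 1.1 | 1.5 | -2 to +2 | 69% |
| No blocking | √113 = 10.6 | √226 = 15.0 | – | – |

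The scheme as written still removes most of the imbalance that unblocked randomization would allow: (3.7/10.6)² = 0.12, so about 88% of the variance within a site is gone.

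**4. Sensitivity to the assumptions.** With 20% of blocks odd, the whole-trial SD is 3.4 (range -6 to +6). With 80% odd, it is 6.6 (-12 to +12). With sites of 150 and 76, it is 5.1. Using only sizes 3 and 6 gives the same mean size and the same share of odd blocks, so the same spread.

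**5. Effect on power.** Take 118:108, a difference of 10 and the edge of the 95% range. The relative efficiency is 4 × 118 × 108 / 226² = 50,976/51,076 = 0.998. After 20% loss:
- 113:113 becomes 90.4 per arm; noncentrality 9 / (19 × √(2/90.4)) = 3.185; t-test power 88.6%.
- 118:108 becomes 94.4 and 86.4; noncentrality 9 / (19 × √(1/94.4 + 1/86.4)) = 3.182; t-test power 88.6%.

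Both lie below 90% because 226 × 0.8 = 180.8 is less than the 188 required. That is a separate matter and does not depend on block size. At the planned 188 evaluable patients, power by the normal formula is 90.1% with equal arms and 90.0% with a difference of 10.

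**The case for a change.** The best case for a change is that size 3 is named in the text, so the mismatch does not depend on how the range is read. A programmer has to supply a rule that the protocol omits, and an auditor cannot confirm that rule from the protocol. A single clause would close the gap, and even sizes would remove the question altogether.

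The first part stands: the rule for the extra place is not written down, and it would be good practice to record it with the randomization list. The rest does not make a case for amendment. The protocol promises a 1:1 ratio, stratification by site and permuted blocks. It does not promise level counts at the end of every block, and a random extra place meets all three promises. Stating the rule would change no result.

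Even sizes are not a clear improvement either. They narrow an imbalance that costs nothing measurable in power, and they make the next assignment easier to predict, with 69% of guesses correct instead of 57%. The treating staff know what they deliver, outcomes are self-reported (sections 10.1 and 10.2), and section 8.5 blinds only the analysts. In that setting predictability can lead to selective enrolment, which is a route to bias. A difference of up to about 10 patients in 226 is not.

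**Conclusion.** The concern does not call for a change. Section 8.4 leaves out one detail, and the stated 1:1 ratio points to the sensible way of filling it: assign the extra place at random. On that reading allocation is unbiased, type I error is unaffected, and the likely imbalance is within about 10 patients of 226, with power unchanged at 88.6% to one decimal. Choosing between 3–6 and even sizes is a fair trade-off between tighter balance and lower predictability, and the plan's choice is defensible.

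The imbalance figures rest on assumed block-size frequencies and site sizes. The variations tried (20% to 80% odd blocks, and sites of 150 and 76) move the whole-trial SD only between 3.4 and 6.6, which does not alter the conclusion. The conclusion would differ only if the list had been built to favour one arm in every odd block, and that would depart from the protocol's own ratio.
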